10.2.1 Workflow

The first patient will be enrolled on the trial and treated at PTV total dose 30 Gy, which is one dose level below the hypothesized MTD. That patient will be entered into the titecrm.sas program and follow-up will begin from start of treatment.

For the purposes of this trial, the patient will be followed from start of treatment until the patient completes 12months of follow-up, has a DLT, or is lost to follow-up. If any of these endpoints occur, the statistician will be notified and the date corresponding to the event will be entered into the program. While there is a maximum follow-up of 6 months for observation of possible toxicities, sometimes patients have a delay in their treatment resulting in the need for a prolonged observation period. This delay will be accounted for, as needed, for this study to ensure a complete 6-month follow-up.

When a new patient is enrolled on the trial, the statistician will be notified of the date of enrollment. At that time the statistician will update the follow-up for all patients currently on the trial and determine the dose that will be administered for the new patient. We will utilize the cumulative time of exposure method, which will allow the contribution of patients with no DLT at this time to be partially weighted consistent with their time observed. We will also utilize the weight function to place more emphasis on the first 6 months follow-up (75% weight) compared to the last 3 months of follow-up (25% weight). At this point, the program provides a summary of the number of patients treated at each dose so far, along with the number of DLTs that have occurred. The posterior probability and 95% credible intervals of dose limiting toxicity for each dose level is calculated. At this point, the model determines the dose level that has an estimated toxicity rate closest to 35% within the 5% admissible margin.

The newly enrolled patient will be enrolled in the corresponding dose level if that dose level is within one dose level from the dose level the most current patient is enrolled on. If the suggested dose level is more than one dose level from the current dose level the next patient will be enrolled on the dose level that is closest to the current level in the direction of the dose level determined from the estimated

Version 09/11/2025 page 42 of 63

posterior probability. This continues until the trial has accrued all 20 patients or, if after 6 patients are enrolled, the estimated posterior.

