10.1.2 TITE-CRM design

The starting dose can have a large impact on the properties of the design. After the trial is completed, most information about the MTD will be obtained if many patients are treated at or near the MTD. Thus, the sooner the choice of dose can converge on the MTD the more effective the trial will be. However, due to the uncertainty of the MTD in the reirradiation of locoregionally recurrent rectal cancer, we will start at the two dose levels lower than the expected MTD to prioritize safety. Therefore, our starting dose for this trial will be PTV total dose of 30 Gy.

The next thing to be considered is the dose escalation rules. For this trial, we will only allow a single dose level escalation per new patient enrolled on the trial.

Version 09/11/2025 page 40 of 63

Therefore, if the previous patient was treated at dose level, d_k , then a new patient can only be treated at dose levels d_{k+1} or lower. In order to determine at which level to treat the new patient, we will use a weighted, cumulative time of exposure approach.

The total length of follow-up for DLT for any patient is 6 months from the start of radiation therapy. In order to efficiently and effectively determine the MTD, we allow for a dose change when the cumulative time of exposure is 6 months. Additionally, since previously published data shows that most toxic events occur within the first 6 months from start of treatment, we also implement a linear weighting function wherein the first 6 months accounts for 75% of the follow-up where the last 3 months attributes 25% of the follow-up information. The dose for the next patient is selected so that the estimated probability at that dose is close to the target level.

A feature of the dose escalation part of the TITE-CRM program is the flexibility in specifying the margin for the dose selection. This allows the selection of the dose level for the next patient that may have an estimated probability of toxicity larger than the target level but less than the target level plus the margin. It finds the dose closest to the target probability even if it has a higher estimated probability. For this trial we set the admissible margin to be 5%, therefore, the MTD will be chosen as the dose that yields a posterior toxicity estimate closest to 35% while being between 30% and 40%. The admissible margin is also used to help determine stopping rules for the trial.

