In order to account for the possibility of poor initial outcomes we will employ a run-in of 6 patients, meaning that the minimum number of treated patients will be 6. If after these 6 patients, or any other time during the trial, the lowest dose level has a posterior probability higher than 40% then the trial will stop.

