10.2 Simulation and Sample Size Calculations

The TITE-CRM manual details methods for utilizing trial simulation in order to obtain estimated posterior probabilities on toxicity estimates. We utilized the simulation program to determine the efficacy of our trial and obtain estimates for needed sample size. While there is no exact power calculation for this type of trial, the effectiveness of the trial's sample size can be determined by looking at the stability of the posterior probability under different prior probabilities.

We ran 1000 simulations under various increasing and decreasing prior probability estimates utilizing the previously described rules and assumptions for this trial and saw sufficient stability in posterior probability estimates with a sample size of 20 patients with a run-in of 6 patients. Simulations showed that approximately 95% of the time the trial will come to completion and the MTD will fall between the 3rd and 5th dose level 89% of the time. Therefore, we will use a fixed sample size of 20 patients for this trial. The posterior probability distribution of these 1000 simulations follow in the next table.

Version 09/11/2025 page 41 of 63

Dose Level	Estimated	Mean
	initial	Posterior
	toxicity	toxicity (SD)
d-1	0.25	0.328 (0.434)
1	0.30	0.38 (0.453)
(Starting		
Dose)		
2	0.35	0.43 (0.463)
3	0.40	0.479 (0.464)

Summary of simulation with estimated posterior probabilities. SD, Standard Deviation

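### Section 10.2.1 limits dose reductions as well as escalations to one level, so after late DLTs the next patient can be treated 5 Gy, occasionally 10 Gy, above the model's choice

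*Combined protocol and SAP*

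**What the plan says.** Section 10.1.2 (TITE-CRM design) sets the step rule for escalation: "we will only allow a single dose level escalation per new patient enrolled on the trial". It adds that after level k "then a new patient can only be treated at dose levels" one above k or anything below, with no limit on how far down the move may go. It describes the selected level as one that may have an "estimated probability of toxicity larger than the target level but less than the target level plus the margin", that is, up to 35% + 5% = 40%. On timing it says "we allow for a dose change when the cumulative time of exposure is 6 months".

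Section 10.2.1 (Workflow) is narrower. The model's level is used directly only "if that dose level is within one dose level from the dose level the most current patient is enrolled on". Otherwise "the next patient will be enrolled on the dose level that is closest to the current level in the direction" of the model's level. This wording works the same way up and down, and the level reached is not checked again against the margin.

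The stopping rule in Section 10.1.2, repeated in Appendix F, applies if "the lowest dose level has a posterior probability higher than 40% then the trial will stop". Section 10.2 says the simulations were run "utilizing the previously described rules and assumptions for this trial", without saying whether reductions were limited.

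**The concern.** The trial uses TITE-CRM because radiation toxicity is delayed (Section 1.7.2). Patients can therefore be escalated before earlier DLTs appear. A cluster of late DLTs at 35 or 40 Gy is when the model may ask for a drop of more than one level, and the workflow then holds back part of it. One more patient with a previously irradiated pelvis is treated above the level the model has just chosen, in a setting where Section 1.7.3 says true organ tolerances are not known. No other rule catches this, because the stop looks only at the 25 Gy level. Section 1.7.2 also states the principle of always treating at the target dose, and the plan gives no reason for departing from it downwards.

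**Working it through.** **Plan's own figures.** The dose table reproduces: BED = nd(1 + d/10) gives 25 × 1.5 = 37.5, 30 × 1.6 = 48, 35 × 1.7 = 59.5 and 40 × 1.8 = 72. The simulation results in Section 10.2 (about 95% completion; MTD between the 3rd and 5th level in 89%) cannot be reproduced: the true curves, accrual, model form and prior are not given, and only four levels are listed. Nothing below rests on them.

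**Step 1: dose gap, from the dose table alone.**

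| Last patient | Model asks for | 10.2.1 gives | Excess |
|---|---|---|---|
| 35 Gy | 25 Gy | 30 Gy | 5 Gy |
| 40 Gy | 30 Gy | 35 Gy | 5 Gy |
| 40 Gy | 25 Gy | 35 Gy | 10 Gy |

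**Step 2: a dated case.** Assumptions not in the plan: power model p_j = s_j^exp(a), a ~ N(0, v), with v = 0.25, 0.5 or 1.34; the level chosen is the one closest to 35% among those at or below 40%. Initial values s = 0.25/0.30/0.35/0.40 come from the Section 10.2 table. Six run-in patients enter Level 1 at months 0 to 9, with 1 DLT. Patients A and B enter Level 2 at 10.8 and 14.3. Two patients enter Level 3 at 15.8 and 17.6. B and both Level 3 patients then have DLTs, and the next patient enters at 19.4.

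With linear 6-month weights every DLT-free patient has full weight by 19.4 (A has 19.4 − 10.8 = 8.6 months), so the likelihood is p₁(1 − p₁)⁵ · p₂(1 − p₂) · p₃². Posterior means:

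| v | Level −1 | Level 1 | Level 2 | Level 3 |
|---|---|---|---|---|
| 0.25 | 29.6% | 34.4% | 39.2% | 44.0% |
| 0.5 | 31.0% | 35.8% | 40.6% | 45.2% |
| 1.34 | 32.5% | 37.2% | 41.9% | 46.5% |

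The model picks 30 Gy each time. Section 10.2.1 gives 35 Gy, estimated at 39.2%, 40.6% or 41.9%. The stop does not fire. Under the tightest prior 40% is not exceeded.

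With 75% of the weight by month 6 and 25% by month 9, A's weight is 0.75 + 0.25 × 2.6/3 = 0.967. Level 2 becomes 39.4%, 40.7% or 42.2%. At v = 1.34, Level −1 is 32.7% and Level 1 is 37.5%, so the model picks 25 Gy and the gap is 10 Gy.

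**Step 3: the other initial values.** Section 10.1.1 gives estimates from 0.05 to 0.25 instead. Three four-level sets in that range were tried with linear 6-month weights: 0.05/0.117/0.183/0.25, 0.05/0.10/0.15/0.20 and 0.10/0.15/0.20/0.25. At v = 0.25 and 0.5 the model picks Level 2 (Level 3 once), so the limit has no effect. At v = 1.34 it picks Level 1 and the workflow gives Level 2 at 40.9%, 40.1% and 40.5%.

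**Step 4: illustrative frequency.** Simulation of 20 patients: first six at Level 1, mean entry gap 36/20 = 1.8 months, uniform DLT times, Section 10.2 initial values, three priors, four true curves and three weight readings, with and without a 6 patient-month requirement before escalation. That makes 72 settings of 1,000 trials. For patients 7 to 20:

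- Drops of two or more levels were requested in 3–33% of trials (2–29% with the exposure requirement).
- At least one assignment above 40% occurred in 0.6–20.5% of trials (0.2–14.1%); the median estimate for those was 41–42% and the maximum 50%.
- Of 13,023 such requests, 1,176 (9.0%) left a 10 Gy gap.
- Limiting escalation only, no MTD selection share moved by more than 2.3 points, and mean DLTs per trial differed by −0.001 to 0.046.

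Smaller runs (300 trials per setting, linear weights) with the three Section 10.1.1-range sets gave such requests in 0–19% of trials for the first set and up to 22–28% for the other two, with an assignment above 40% in 0–20% of trials.

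**The case against.** The strongest reply is that this is a preference between two acceptable step rules. The forced dose is always below the previous patient's, any excess over 40% is usually a point or two, and single steps dampen swings on small counts. Under-treatment was not measured here, and Section 1.2 regards low reirradiation doses as generally insufficient for gross disease. All of this stands as a limit on size. It does not justify the limit, because the model's choice already weighs the data and MTD selection hardly changes without it.

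A second reply is that the dated case depends on the Section 10.2 initial values. That also stands: with Section 10.1.1 values it needs the widest prior.

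A third concerns the exposure rule, which speaks of a dose change, not an escalation. Counted per level, Level 3 has at most 3.6 + 1.8 = 5.4 patient-months at month 19.4. Read literally, no change would be allowed and the next patient would stay at 40 Gy under either step rule. The fix therefore has to cover this rule too.

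Three stronger readings are tempting but unsupported:

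- **The two sections contradict each other.** They do not: a one-level drop also satisfies Section 10.1.2.
- **The workflow breaches a stated 40% ceiling.** Section 10.1.2 uses 40% to describe level selection and states no separate ceiling on every assignment.
- **The sample-size simulation is invalid.** The documents do not show which step rule it used.

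**Conclusion.** The point holds as a minor design weakness. The 5 and 10 Gy gaps follow from the text and the dose table; 10 Gy arises only when the model asks for 40 to 25 Gy. It would be wrong to infer that such patients are routinely treated 10 Gy too high or above 40%: most gaps are 5 Gy, and whether 40% is passed depends on the prior, the follow-up weights and which initial estimates apply. All frequencies rest on assumed model, accrual and true toxicity rates, so confidence in them is moderate. What makes a change worthwhile is the balance: the downward limit adds a little exposure above the model's choice, with almost no gain in MTD selection.

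**What to change.** In Section 10.2.1, apply the one-level limit to escalation only. A suggestion more than one level above the current level is cut to one level above; a suggestion below the current level is assigned directly. State that this applies after the six-patient run-in at Level 1 and leaves same-level replacement (Section 10.2.3) unchanged. In Section 10.1.2, say that the 6-month cumulative-exposure requirement governs escalation and does not delay a reduction.

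A blanket 40% ceiling is not needed. After the run-in, and leaving replacements aside, the model's level is at or below 40% or the trial has stopped, under the selection rule assumed above. Such a ceiling would also clash with the run-in: with v = 0.25, 2 DLTs in 3 patients put Level 1 at 41.4% and Level −1 at 36.6%, so the trial continues while the Schema still requires Level 1.

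Check that the titecrm.sas setting matches, and confirm which step rule the Section 10.2 simulation used; re-run it only if it limited reductions. The cost is a few sentences and a program check, with no extra patients or procedures. The downside is slightly larger downward swings on small counts, so a few patients may be treated at a lower dose.

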
10.2.2 Recommended Phase 2 Dose

The MTD will be estimated using the proposed TITE-CRM model. After the phase I study, the MTD will be chosen as the dose that yields a posterior toxicity estimate closest to 35% while being between 30% and 40%.

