1.7.2 Scientific Rationale for Study Design

The standard phase I 3+3 dose-escalation design is poorly suited for trials of radiotherapy, for which toxicities may occur up to several months after treatment. In this case, the 3+3 design, or any design that requires all patients to have completed observation for toxicity, is subject to openings and closings as patients present after a dose level potentially has filled, but before sufficient time has elapsed to be certain that treatment has not produced dose-limiting toxicities (DLT).

As such, dose escalation for this trial will be guided by the Time-to-Event Continual Reassessment Method (TITE-CRM). TITE-CRM seeks to determine the target dose, defined as the dose most closely identified with the target rate, which is the largest acceptable probability of toxicity, determined a priori by the investigators based on the relative costs and benefits of the treatment (typically between 5% and 25%). As the trial progresses and patients do or do not experience toxicities at different doses, the estimates of probability of toxicity are recalculated using a Bayesian expectation, and subsequent patients are assigned to doses under the principle to always treat at the target dose.

In a Monte Carlo simulation of 60,000 phase I trials comparing 3+3 design to TITE-CRM in studies with delayed toxicity, the TITE-CRM trials were significantly shorter when toxicity observation times are long, treated more patients at or above the maximum-tolerated dose, identified the MTD more accurately, but did not expose patients to significant additional risk (97). Additionally, given that TITE-CRM concentrates most of the accrual around the target dose, early estimates of efficacy are possible.

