10 STASTISTICAL CONSIDERATIONS

10.1 Phase I Methodology for Primary Endpoint

10.1.1 Background of TITE-CRM and trial rules

The Time-to-Event Continual Reassessment Method (TITE-CRM) proposed by Cheung and Chappell is an adaptive Phase I design (98). In a TITE-CRM clinical trial, patients enroll as they become available to be studied. Each participant is assigned to a dose level from a set of dose levels pre-defined by investigators and is monitored for DLTs over time. The design is adaptive in that the dose level assigned to a newly enrolled patient depends on the dose level assignments and dose limiting toxicity outcomes of the patients already in the study. A patient's observation period ends at the occurrence of a DLT or, if a DLT does not occur, after a fixed time T of follow-up. The trial ends when a fixed number of patients, n, have been observed. Once the final patient has been observed, the MTD can be estimated using the available data.

Version 09/11/2025 page 39 of 63

The TITE-CRM differs from the traditional CRM in that the estimation process is weighted to account for the proportion of the observation period that each currently enrolled patient has been observed. By not requiring complete observation before the enrollment of the next patient, new participants can be assigned a dose and begin evaluation as they become available, subsequently shortening the overall duration of the study.

The Biostatistics Unit at the University of Michigan Comprehensive Cancer Center has developed a program titecrm.sas for SAS 9 (SAS Institute, Inc.; Cary, NC) that makes all of the calculations necessary to determine dose allocation of a trial in real-time. They have also developed simulation programs that allow the user to determine the efficacy of the trial based on *a priori* estimates of the probabilities of toxicity and necessary sample sizes.

In order to properly utilize this type of trial, a few assumptions and many rules must be determined before the start of the trial. The main assumption that must be determined is how many different dose levels will be included in the trial and *a priori* estimates of the probability of a DLT at each of those dose levels. For this trial, we have 5 dose levels listed below $(d_1,...,d_5)$, with initial toxicity probability estimates $(p_1,...,p_5)$ ranging from 0.05 to 0.25, respectively. The following table shows the dose design with associated estimated probabilities of toxicity.

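### If the SDs in the Section 10.2 simulation table are the spread across simulated trials, the table cannot be squared with the 95% and 89% figures that justify 20 patients

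*Combined protocol and SAP*

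**What the plan says.** **The MTD rule.** Section 10.2.2 states that "the MTD will be chosen as the dose that yields a posterior toxicity estimate closest to 35% while being between 30% and 40" per cent. Section 10.1.2 gives the same window, built from a 35% target and a 5% margin.

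**The stopping rule.** The end of 10.1.2, repeated in Appendix F, stops the trial if the lowest level's posterior toxicity exceeds 40%, after the 6-patient run-in or at any other time.

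**The simulations.** Section 10.2 says they were run "utilizing the previously described rules and assumptions for this trial" and that the authors "saw sufficient stability in posterior probability estimates with a sample size of 20 patients". About 95% of trials reached completion, and "the MTD will fall between the 3rd and 5th dose level 89% of the time". The size of 20 follows from this. The table is introduced with: "The posterior probability distribution of these 1000 simulations follow in the next table".

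**The table.** It has four levels. Initial estimates are 0.25, 0.30, 0.35 and 0.40. Mean posterior toxicity (SD) is 0.328 (0.434), 0.38 (0.453), 0.43 (0.463) and 0.479 (0.464). The caption expands SD only as standard deviation.

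**The levels in the text.** Section 10.1.1 announces five dose levels with initial estimates "ranging from 0.05 to 0.25, respectively", above a table that lists four.

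**The concern.** The plan says that no exact power calculation exists for this design, so the simulations are the only support for 20 patients. The 95%, the 89% and the table are presented as results of the same 1000 runs and should agree with one another.

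The printed SDs are close to the largest that a quantity between 0 and 1 can have. Taken as the spread across trials, they put most simulated estimates near 0 or 1. Few could then lie between 30% and 40%, and many would have the lowest level above 40%. That conflicts with 95% completion and with an MTD named in at least 89% of trials.

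If the figures are wrong or belong to another design, the plan has no usable operating characteristics for the rule that produces its primary result. A reader cannot tell how often the trial will stop early, name an MTD, or finish with no level in the window. The last case matters because no section says what would then be reported.

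**Working it through.** **What can be reproduced.** The 95% and 89% cannot be regenerated. The documents give no true toxicity rates, accrual rate, dose-toxicity model or prior variance. The check therefore asks whether the table permits them.

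**Inputs.** Means m and SDs s from the 10.2 table, the 30-40% window (10.1.2, 10.2.2) and the 40% stop (10.1.2). Let X be a level's final estimate in a simulated trial, between 0 and 1, and read s as the SD of X across trials.

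**Step 1: size of the SDs.** The largest possible SD is √(m(1−m)).

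**Step 2: one level in the window.** E[X(1−X)] = m − m² − s². Between 0.30 and 0.40, X(1−X) is at least 0.30 × 0.70 = 0.21. So P(0.30 ≤ X ≤ 0.40) ≤ (m − m² − s²)/0.21.

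| Level | m (s) | Largest SD | s / largest | m − m² − s² | Ceiling on P(30-40%) |
|---|---|---|---|---|---|
| -1 | 0.328 (0.434) | 0.469 | 92% | 0.03206 | 15.3% |
| 1 | 0.38 (0.453) | 0.485 | 93% | 0.03039 | 14.5% |
| 2 | 0.43 (0.463) | 0.495 | 94% | 0.03073 | 14.6% |
| 3 | 0.479 (0.464) | 0.500 | 93% | 0.03426 | 16.3% |

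Adding the ceilings bounds the chance that any tabulated level is in the window: **60.7%**, or 62.5% allowing for rounding in the table. No dose ordering is assumed.

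**Step 3: Level -1 above 40%.** X(X − 0.4) is at most 0 when X ≤ 0.4 and at most 0.6 otherwise. So

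P(X > 0.4) ≥ (m² + s² − 0.4m)/0.6 = (0.10758 + 0.18836 − 0.13120)/0.6 = 0.16474/0.6 = **0.275** (0.274 with rounding).

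If Level -1 is the lowest simulated level, these trials meet the stopping criterion. Completion is then at most 1 − 0.274 = 0.726, about **73%**, against 95%. This counts as stopped a trial that crosses 40% only at its final estimate.

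**Step 4: Level 3 below 30%.** Put Y = 1 − X, with mean 0.521 and SD 0.464. By the same argument

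P(Y > 0.7) ≥ (0.521² + 0.464² − 0.7 × 0.521)/0.3 = (0.27144 + 0.21530 − 0.36470)/0.3 = **0.407**.

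**Step 5: if estimates rise with dose.** Level -1 above 40% puts every level above the window, and Level 3 below 30% puts every level below it. The two events exclude each other, so at most 1 − 0.407 − 0.275 = 0.318 of trials have a level in the window (0.319 before rounding the terms, about **32%**). With an unlisted fifth level above Level 3, only the first event rules out the window: 1 − 0.275 = 0.725, about **73%**.

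**Step 6: comparison.** An MTD at the 3rd to 5th level in 89% of trials requires one to be named in at least 89%. If the 89% applies only to completed trials, the share is 0.89 × 0.95 = 0.846. Ceilings of 61-63%, 32% and 73% are all lower.

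**Step 7: are such SDs plausible?** Illustrative 20-patient simulations of the four levels were run under assumed one-parameter models and a range of prior variances. Across-trial SDs were 0.11-0.20 in one set, with the table's initial estimates taken as true. They were about 0.06-0.14 in a second set with full follow-up and several assumed sets of true rates. The table prints 0.434-0.464.

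**The case against.** The strongest reply is that the SD column cannot be the spread across trials, since realistic runs give less than half the printed values. The table would then be mislabelled or mistaken, and the ceilings would describe that error rather than the trial. This stands as a limit on what the ceilings mean. It does not rescue Section 10.2, which introduces the table as the distribution from the same simulations and uses stability of these estimates to justify 20 patients.

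A reader might infer that the design names an MTD in only 32% of trials, or that finding no level in the window is the usual outcome. The documents do not support that. The 32% needs estimates ordered by dose, and 10.2 mentions both increasing and decreasing prior estimates. It also needs the doubtful reading of the SDs. In the second set of illustrative runs, 25% to 77% of trials completed with a level in the window, depending on assumed rates and prior variance.

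A reader might also infer that the 89% came from a rule without the window. Section 1.7.2 describes the target dose as "defined as the dose most closely identified with the target rate", and 10.1.2 says of the program: "It finds the dose closest to the target probability even if it has a higher estimated probability". But 1.7.2 is a general account of the method, 5.2 refers the MTD definition to Section 10, and 10.2 says the described rules were used. With five levels and assumed true rates from 0.02 to 0.55, the 30-40% rule named the 3rd level or higher in 81-86% of illustrative trials. A figure near 85% is therefore attainable under the written rule.

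**Conclusion.** The simulation evidence for 20 patients is internally inconsistent as written. Read as spread across simulations, the table allows at most about 73% completion against the stated 95%. It allows a tabulated level in the MTD window in at most 61-63% of trials, against an MTD at the 3rd to 5th level in 89%. The completion conflict does not depend on the MTD window, so the window is not shown to be the fault.

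The assumptions are:

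- the SD column is the across-trial SD of the estimates to which the rules are applied;
- Level -1 is the lowest simulated level, for the completion figure;
- estimates rise with dose, for the 32% and 73% window ceilings only. An unlisted fifth level with no ordering would leave no ceiling on the window share.

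If the SD column is something else, the numerical conflict falls away, but the column then needs a definition or a correction. Whatever it is, two faults remain. The text describes five levels at 0.05-0.25 and the table four at 0.25-0.40, and a 3rd-to-5th-level result cannot be read from a four-level table. Nor does any section say what is reported if no level lies in 30-40%.

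**What to change.** 1. Re-run the simulations for the four tabulated levels and their initial estimates, with the MTD rule of 10.1.2 and 10.2.2 and the 40% stop as written.
2. State the true toxicity rates used and what the SD column measures.
3. Report the share of trials stopped early, the share ending with no level in 30-40% (all below, and otherwise, shown separately), and the distribution of the MTD by level.
4. Correct the table, the level count, and the 95% and 89% figures to match. Reconcile 10.1.1 with 10.2 on levels and initial estimates.
5. Align the general wording in 1.7.2 with Section 10, and state in advance what will be reported if no level lies in 30-40%.

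The window, dose levels, patient assignment and stopping rule remain the sponsor's decisions, and nothing here asks for them to change. The cost is a simulation run and edits to a few sections, with no change to conduct. The downside is that the restated figures may be less favourable to 20 patients, and the plan would have to say so.
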